## **18. COMPLIANCE, PROTOCOL AMENDMENT AND DEVIATION**

### **18.1 Compliance**

An application dossier for the commencement of a clinical trial, must be submitted to the national competent authorities of Poland and the Ethics Committees, prior to the start of the study. The authorization to conduct the clinical trial must be obtained prior to initiation of any screening activities, including ICF signature.

It is very important that no modifications to the protocol be made without prior approval from the Sponsor. Changes that significantly affect the safety of the patients, the nature, the scope and the scientific integrity of the study will require IRB/IEC notification/approval before their implementation. Exceptions are cases where the modification is necessary to abrogate an apparent immediate risk to the patients. The Sponsor's designee will submit all protocol modifications to IRB/IEC and the required regulatory authorities. When there is a need for immediate deviation from procedures enunciated in the protocol, the Investigator will contact the Sponsor to discuss the course of action and possible alternatives, if at all possible, before any implementation of changes. Any deviation from protocol must be fully documented in the source documentation and in the study documentation on protocol deviations.

### **18.2 Protocol Amendment**

Administrative amendments to the protocol will be classified as amendments of typographical errors, clarifications of confusing wording, name changes, and minor modifications that have no impact on the safety of the patients or the science of the study. Administrative amendments will be submitted to the IRB/IEC for information only. JSS Medical Research will ensure that acknowledgement is received and filed. Any other amendment will be classified as a substantial amendment and will be submitted by the Sponsor's designee to the appropriate regulatory authorities and the IRBs/IECs for approval.

### **18.3 Protocol Deviation**

Should a protocol deviation occur, the Sponsor must be informed as soon as possible. Important protocol deviations and their reasons will be summarized in the clinical study report. In accordance with applicable regulatory authority mandates, the Investigator is responsible for reporting protocol deviations to the IRB/IEC.

## 19. STUDY TERMINATION

At any time, the Sponsor may terminate this study in its entirety or at a specific clinical site. In addition, for reasonable cause, the IRB/IEC and/or the Investigator at a clinical site may terminate the study at their center. In such cases, the Sponsor should be informed immediately and if at all possible, before implementation.

Conditions that may lead to reasonable cause and warrant termination include, but are not limited to:

- Investigator noncompliance and/or lack of adherence to protocol procedures;
- Unsatisfactory patient enrollment;
- Lack of evaluable and/or complete data;
- Potentially unacceptable risk to patients;
- Changes in the Sponsor's drug development plans;
- Decision by regulatory authorities.

The reason(s) for clinical study termination must be properly documented. If the trial is prematurely terminated or suspended for any reason, the clinical site or the qualified investigator (or delegate) should promptly inform the trial subjects, should assure appropriate therapy and follow-up for the subjects and should inform the regulatory authority(ies) when required.

## 20. ETHICAL CONSIDERATIONS

This study will be conducted in compliance with the study protocol, the ethical principles that have their origins in the Declaration of Helsinki, ICH Guideline E6 for Good Clinical Practice (GCP), the FDA GCP Code of Federal Regulations (CFR) Title 21 (part 56), the European regulation EU 536/2014, the Tri-Council Policy Statement (Canada) and Division 5 part C section of Health Canada.

IRB/EC committees will review and approve this protocol and informed consent forms. Substantial amendments to the protocol and ICF will be submitted to the IRB/EC and written approval will be obtained prior to implementation. All patients must provide signed informed consent where applicable, before participation in the study. Before screening activities commence, each subject will be given a copy of the ICF to read, as well as a full explanation of the purpose of the study, the procedures to be carried out, and the potential AE(s). Once this essential information is provided to the subject and the physician in charge or delegate has the conviction the subject understands the implications of participating in the study, and if the subject chooses to continue the screening process, they will be requested to sign and date a properly executed ICF. Subjects will be assured they may withdraw from the study at any time without jeopardizing their medical care or future study participation (for which they qualify). Subjects will be given a signed copy of the ICF. If an amended or revised ICF is introduced during the study, each subject's further consent must be obtained.

This study will be performed by qualified clinical investigators and in accordance with GCP. The study specifically incorporates all of the following features:

- Multicenter, randomized study design;
- Prospectively stated objectives and analytical plan;
- Accepted, pre-specified outcome measures for safety and efficacy;
- A detailed protocol to promote consistency across sites;

- Compliance with current GCP, with assessment via regular monitoring;
- Quality assurance procedures performed at study sites and during data management to ensure that safety and efficacy data are adequate and well documented.

This protocol and the ICF will be submitted to an Institutional Review Board (IRB) (or Independent Ethics Committee (IEC)) prior to initiation of the study and the study will not start until the Board has approved the documents. Notification of the Board's approval will be appended to the final report. The study will only be conducted at sites where IRB/IEC approval has been obtained. The protocol, Investigator's Brochure, sample ICF, advertisements (if applicable), written information given to the patients, safety updates, annual progress reports, and any revisions to these documents will be provided to the IRB/IEC by the Sponsor's designee, as allowable by local applicable laws and regulations.

The investigators and the Sponsor will preserve the confidentiality of all subjects taking part in the study, in accordance with GCP and local regulations. Subjects should be identified by a unique subject identifier on all study documents provided to the sponsor. In compliance with local regulations/ICH GCP Guidelines, it is required the investigator and institution permit authorized representatives of the company, of the regulatory agency(s), and IRB access to review the subject's original medical records for verification of study-related procedures and data. The investigator is obligated to inform the subject that his/her study-related records will be reviewed by the above-named representatives without violating the subject's confidentiality.

## **21. FINANCE AND INSURANCE**

Financial aspects of the study are addressed in a separate clinical study agreement.

The Investigator/institution is required to have adequate current insurance to cover claims for negligence and/or malpractice according to national regulations. The Sponsor's designee will provide insurance coverage for the clinical study as required by national regulations. This should include sufficient insurance coverage should any serious events or deaths result, either directly or indirectly, from the execution of the present protocol.

The present article is not to be interpreted as engaging the Sponsor's responsibility in the event of fault or negligence of the subjects, investigators, or any persons or employees under the control of the clinical site.

## **22. PUBLICATION POLICY AND CLINICAL STUDY REPORT**

### **22.1 Confidentiality and Publication Policy**

Both the use of data and the publication policy are detailed within the clinical study agreement.

Any and all scientific, commercial, and technical information disclosed by the Sponsor in this protocol or any other documents and communications should be considered the confidential and proprietary property of the Sponsor. The Investigator shall hold such information in confidence and shall not disclose the information to any third party except to the Investigator's staff on a "need to know" basis, as long as the said staff has been made aware that the information is confidential and who are bound to treat it as such.

The Investigator shall not use any and all information for any purpose other than determining interest in performing the study and, if the parties decide to proceed with the study, for the purpose of conducting the study. The

Investigator understands that the information developed from this clinical study will be used by the Sponsor for the development of the study drug and therefore may be disclosed as required to other clinical Investigators, potential and current business partners and associates, Health Canada, the FDA, and possibly other regulatory agencies. The Investigator also understands that, to allow for the use of the information derived from the clinical study, he/she has the obligation to provide the Sponsor with complete results and accompanying data developed in the study.

No publication or disclosure of study results will be permitted except under the terms and conditions of a separate written agreement between the Sponsor and the Investigator and/or the Investigator's institution.

## **22.2 Clinical Study Report**

A full clinical study report, written in accordance with the ICH E3 Guideline, will be submitted in accordance with local regulations.

**APPENDIX 1: Sample Bowel Movement and BSFS Diary**

**Daily Symptom and Stool Diary – Period 1**

DAY	DATE (e.g. Monday 05/Jun/18)	Loperamide taken today (e.g. 2 pills)	Time Study Drug Taken (24 hr clock)	STOOL FORM AND TIME (Stool Form = 1 to 7 from chart below; Time = time of stool, 24 hour clock (e.g. 15:30 for 3:30 pm))												
				1 st	2 nd	3 rd	4 th	5 th	6 th	7 th	8 th	9 th	10 th	11 th	12 th	
1				Form												
				Time												
2				Form												
				Time												
3				Form												
				Time												
4				Form												
				Time												
5				Form												
				Time												
6				Form												
				Time												
7				Form												
				Time												

1  Separate hard lumps, like nuts	4  Like a sausage or snake, smooth and soft	7  Watery, no solid pieces
2  Sausage shaped but lumpy	5  Soft blobs with clear cut edges	
3  Like a sausage or snake, but with cracks on its surface	6  Fluffy pieces with ragged edges, a mushy stool

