## **7. STUDY DESIGN**

### **7.1 Endpoints**

#### **7.1.1 Primary Endpoint**

The primary endpoint will be the change in the weekly frequency of bowel movements, measured between baseline and the second week of treatment (ie. Days 8 to 14 and Days 36 to 42). Efficacy will be assessed as the overall difference vs baseline as well as the difference between the two treatment doses.

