**8.1 Inclusion Criteria**

1. Adult, ambulatory male and female subjects
2. Provision of signed and dated informed consent form (ICF)
3. Age ≥ 18 years and ≤ 80 years
4. Stable SBS, of:
  - a. Non-surgical origin; OR
  - b. Surgical origin where the last surgical ileal resection was performed at least 6 months prior to enrolment

5. Partial, Home Parenteral Nutrition and/or parenteral fluids are allowed, at a maximum frequency of 6 times a week throughout the trial, as long as the regimen has been stable for at least 2 weeks prior to screening and is expected to remain unchanged during the study
6. At least 50 % of the colon being intact
7. Intact duodenum
8. BMI  $\geq$  18
9. Presence of stable chronic diarrhea for at least 3 months prior to enrolment as evidenced by medical history
10. Presence of stable chronic diarrhea during the 2-week screening diary period before randomization, as evidenced by completion of a screening diary demonstrating:
  - a. Mean daily production of at least 3 soft or watery stools (BSFS scores 6 or 7); **or**
  - b. More than 3 bowel movements per day on average with >25% of them being BSFS type 6 or 7
11. Stated willingness to comply with all study procedures and availability for the duration of the study
12. Clinical laboratory values within the laboratory's stated normal range; if not within this range, they must be without clinical significance, as determined by the investigator
13. Female subject must meet one of the following criteria:
  - a) Participant is of childbearing potential and agrees to use one of the accepted contraceptive regimens from at least 30 days prior to the first study treatment administration through to at least 30 days after the last dose of the study treatment. An acceptable method of contraception includes one of the following:
    - a) Abstinence from heterosexual intercourse
    - b) Systemic contraceptives (combined birth control pills, injectable/implant/insertable hormonal birth control products, transdermal patch)
    - c) Intrauterine device (with or without hormones)
    - d) Condom with spermicide
  - b) Participants of non-childbearing potential, defined as surgically sterile (i.e. has undergone complete hysterectomy or bilateral oophorectomy) or is in a menopausal state (i.e. at least 1 year without menses prior to the first study drug administration) are eligible

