#### 9.2.1 Screening and Eligibility Assessments (Visit 1, Day -15)

On Day -15 prior to randomization, interested SBS patients will undergo a screening session, Visit 1. Patients will arrive in the fasted state (i.e. fast for 4 hours before visit). This visit is comprised of the following elements:

1. Verification of identity and demographics (age, gender, race);
2. Confirmation of the SBS diagnosis will be obtained, with proper medical history data;
3. Description of the type and extent of intestinal surgical resection will be provided (if applicable);
4. Verification of all inclusion and exclusion criteria;
5. Collection of medical history including history of intestinal surgical resection or other possible cause of SBS, all current medications and therapies, non-prescription drug intake, and HPN if still administered. Particular attention will be paid to obtaining the history of diarrhea in the 3 months prior to screening, as well as prohibited drugs;
6. Measurement of body weight and height, and calculation of BMI;
7. Measurement of vital signs including heart rate, blood pressure and body temperature;
8. Complete physical examination;
9. An ECG will be performed;
10. All safety laboratory tests including hematology, serum chemistry, pregnancy test (if applicable) and urinalysis (dipstick). Screening laboratory results must be available and reviewed by the Investigator before randomization.
11. Patients will be given a bowel movement (BM) and BSFS diary, in which they will need to record daily the number of stools and their form, using the BSFS. Proper instructions will be provided for the use of the BSFS. Patients will be instructed to start recording in this Screening diary at Day -14 and to fill it out daily until Day -1 inclusive, in order to establish a baseline and confirm patients' eligibility.
12. All screening results must be available prior to Day 0 randomization so that the study Investigator can determine eligibility.
13. From screening to the first dose of the study, AEs will be recorded as screening events or as part of the medical history, as applicable.

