### 12.2 Bristol Stool Form Scale

The Bristol Stool Form Scale (BSFS) is a diagnostic medical tool designed to categorize and score the form of human stools into seven categories (30,31). It is used mostly in clinical research. It is sometimes also referred to as the Bristol stool chart (BSC), Bristol stool form scale, or BSF scale.

It was developed at the Bristol Royal Infirmary as a clinical assessment tool in 1997, and is widely used as a research tool to evaluate the effectiveness of treatments for various diseases of the bowel, especially Irritable Bowel Syndrome and chronic constipation. BSFS scores of 6 or 7 indicate diarrhea.

Figure 2 - Bristol Stool Chart

Reference: Lewis and Heaton (1997)

All patients will be asked to examine their stools at every bowel movement and to provide a general estimation of their form, according to the Bristol Stool Chart. This will be done at every bowel movement, every day as per the Schedule of Activities. This information will also be recorded in the patient diary.

The Mean Diarrhea Composite Index ([weekly bowel movement frequency X mean daily BSFS score] + loperamide use [weekly mg X 3]) at baseline and during the second week of treatment (i.e. Days 8-14, and Days 36-42) will also be estimated.

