#### **14.1 Sample Size Determination**

This is a cross-over trial in which patients will be randomized to two different sequences of treatment.

The primary outcome measure will be the change in the weekly frequency of bowel movements between baseline and Week 2 of treatment (ie. Days 8 to 14, and Days 36 to 42). Efficacy will be assessed as the difference vs. baseline as well as the difference between the two treatments.

Given that this is a cross-over study, patient will serve as their own control and the statistical analysis will be based on matched comparisons. Depending on the distribution of the difference between the two treatments the parametric Paired Student's t-test, or non – parametric Wilcoxon's sign rank test will be used. The current sample size computation will be based on the parametric test, since this is more conservative and hence demanding of a higher sample size.

The following assumptions have been employed:

- i. The mean change in the lesser efficacious treatment will be 4 bowel movements per week.
- ii. The SD for the change in bowel movements per week will be 2.0 based on extrapolation of results from the literature (32).
- iii. The correlation of the changes between the two treatments will be 0.80 given that there is a strong patient effect on bowel movements. Hence the SD of the difference between treatment groups is 1.265 assuming an SD of 2.00 for each treatment group.
- iv. The significance level will be 0.05.
- v. The power of the study will be 80%.
- vi. The effect size to be detected will be between 10% and 25%.
- vii. Adjustment of 20% has been considered to compensate for attrition.

The following table describes the sample size requirements (number of patients) for the study by different effect size.

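### The sample diary has room for 12 stools a day, with no overflow line and no daily total, so the primary count can be truncated on days above 12

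*Combined protocol and SAP*

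**What the plan says.** Section 7.1.1 defines the primary endpoint as the "change in the weekly frequency of bowel movements, measured between baseline and the second week of treatment". Section 12.1 takes the count from the patient's diary, kept daily from Day -14 to Day 42, and describes no other source.

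The written instructions set no maximum. At screening (Section 9.2.1), and again for Period 1 (Section 9.2.3), patients are to "record daily the number of stools and their form, using the BSFS". Section 12.2 asks for the form of each stool: "This will be done at every bowel movement, every day as per the Schedule of Activities".

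The only diary page shown is headed "APPENDIX 1: Sample Bowel Movement and BSFS Diary". Its row for each day is labelled "STOOL FORM AND TIME (Stool Form = 1 to 7 from chart below; Time = time of stool, 24 hour clock" and has columns numbered 1st to 12th. It has no field for the number of stools, no overflow line and no instruction for a 13th stool.

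Inclusion criterion 10 (Section 8.1) sets only lower limits: "Mean daily production of at least 3 soft or watery stools (BSFS scores 6 or 7" under 10a, or "More than 3 bowel movements per day on average with >25% of them being BSFS type 6 or 7" under 10b. No exclusion criterion in Section 8.2 limits frequency. Sections 12.1 and 14 give no rule for a day with more than 12 stools.

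**The concern.** The text asks for a daily number, but the form has nowhere to write one. The number has to be derived from the filled columns, and these stop at 12 per day, or 12 × 7 = 84 per week. If stools beyond the 12th are not recorded, the higher of two counts loses more than the lower one, so a patient who improves appears to improve less. The number of stools with BSFS 6 or more and the Diarrhea Composite Index (Section 7.1.3) draw on the same columns.

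The loss cannot be repaired later, because a stool that was never written down cannot be recovered at analysis. The trial plans 18 patients and about 15 evaluable, so the comparison between doses has little spare power.

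**Working it through.** **Inputs from the protocol.** Twelve entries per day (Appendix 1). Fall on the less effective dose 4 per week, SD of the change 2.0, correlation 0.80, 80% power, 20% attrition (Section 14.1); "The significance level will be 0.05". Dose difference to detect 1.0 per week, with 15 patients in Table 3 and 18 recommended.

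**Assumptions, because the documents give no figures.** The distribution of baseline frequency, the day-to-day variation, and that stools beyond the 12th are not recorded at all.

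**1. The plan's own figure.** SD of the paired difference = √(2 × 2.0² × (1 − 0.80)) = 1.265. A two-sided paired t-test at 0.05 for a difference of 1.0 needs 15 patients (power 0.81), and 15 × 1.2 = 18. All 16 rows of Table 3 reproduce.

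**2. Loss in the change from baseline.** With daily count X of mean μ, the expected number of stools lost per week is L(μ) = 7 × E[max(X − 12, 0)]. A true fall of 4 per week takes the daily mean from μ to μ − 4/7, so the recorded fall is 4 − [L(μ) − L(μ − 4/7)]. For Poisson X:

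| Baseline mean per day | Lost per week at baseline | Lost per week in week 2 | Recorded fall per week |
|---|---|---|---|
| 8 | 0.91 | 0.54 | 3.63 |
| 10 | 3.72 | 2.63 | 2.91 |
| 12 | 9.61 | 7.59 | 1.98 |
| 14 | 18.63 | 15.77 | 1.14 |

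Most of the loss occurs in both weeks and cancels. The bias in the change is 4 minus the last column: about 0.4, 1.1, 2.0 and 2.9 per affected patient.

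**3. Sensitivity to day-to-day variation.** Across Poisson counts and normal counts with SD 1 or 2, the recorded share of a fall of 4 is 90–100% at a mean of 8 per day, 72–100% at 10, 49–62% at 12, 4–29% at 14 and 0–14% at 16.

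**4. How high the mean must be.** A mean above 12 is not needed. Under Poisson variation the chance that a given day exceeds 12 is 0.064 at a mean of 8, so 1 − (1 − 0.064)⁷ = 0.37 of weeks contain such a day. At a mean of 10 the daily chance is 0.208, and about 0.8 of weeks do.

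**5. Effect on the group results.** Take a patient whose recorded change is zero on both doses.
- Change from baseline: one such patient of 15, with a true fall of 4, lowers the mean by 4/15 = 0.27. Simulated power for the low dose against baseline stays at about 1.00 with up to four such patients.
- High minus low: Section 12.1 measures against the week before randomization, and Section 14 defines baseline as before the first dose. A baseline shared by both periods drops out of the dose contrast. The patient loses only their own dose difference, so the mean falls by 1.0/15 = 0.07.
- Simulated power for the dose contrast:

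| Fully capped patients | 15 evaluable | 18 evaluable |
|---|---|---|
| 0 | 0.81 | 0.89 |
| 1 | 0.78 | 0.87 |
| 2 | 0.74 | 0.84 |
| 3 | 0.70 | 0.81 |

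**The case against.** The strongest reply is that no rule says a 13th stool is not counted. Appendix 1 is a sample showing seven days of one diary, whereas the real diaries cover 14 days. The text asks for every stool, diaries are checked at each visit (Section 11), and discrepant data are queried (Section 17). A patient could write in the margin. This stands to the extent that truncation is a risk and not a documented rule. It does not remove the risk: whether a marginal entry is made and then entered in the e-CRF is left to the patient and site, and a check of a form with twelve filled columns gives no sign that anything is missing.

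A second reply also stands: nothing in the documents shows that any enrolled patient will exceed 12 on any day. Eligibility starts at about 3 per day.

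A reader might also think that criterion 10a makes matters worse, because a patient who meets 10a but not 10b has either exactly 3 stools a day, all loose, or at least 3/0.25 = 12 a day. The arithmetic is right, but it does not bear on this point. Such patients at 12 or more have at most 25% loose stools, and high-frequency patients with a larger loose share already enter through 10b.

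**Conclusion.** The gap between form and instructions is real, and closing it is a cheap improvement. It is not a flaw that threatens the trial. If excess stools go unrecorded, a true fall of 4 per week would appear as about 3.6, 2.9, 2.0 and 1.1 at baseline means of 8, 10, 12 and 14 per day (Poisson counts). The bias is toward no effect. It is small for the dose comparison, about 0.07 per week for one fully capped patient of 15, and nil if no patient exceeds 12 on any day. The number of patients exposed is unknown.

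Two stronger readings are not supported. One is that counts are capped and the improvement of severe patients is lost. The documents show only that counts can be truncated, and the change is attenuated, with near-total loss only at about 14 to 16 per day or more. The other is that a few capped patients could cancel the planned dose difference. A patient who falls from 14 to 12.5 per day, with every day above 12, would lose 1.5 × 7 = 10.5 per week, or 10.5/15 = 0.7 on the mean of 15. That is a loss in change from baseline in a patient constructed to show zero change, and it should not be set against the 1.0 between doses.

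**What to change.** In Appendix 1 and in all four diaries (Screening, Period 1, Washout, Period 2), add for each day an overflow line for stools beyond the 12th and a box for the total bowel movements that day. In Section 12.1, state that the weekly count is the sum of these daily totals, and say how a total that disagrees with the number of individual entries is to be resolved.

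The cost is a reprint of the diary, one e-CRF field if it is not already there, and the work of reconciling totals with entries. No change to eligibility, visits or sample size is needed.
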